6.1.1 Withdrawal of subjects due to non-compliance/ adherence

The investigator shall withdraw the patients from both groups of the study if

- Fasting blood sugar rises > 126 mg. /dl, or 2 hours OGTT blood sugar level increases > 199 mg/dl and are not controllable within 90 days.
- Any serious complication develops which requires urgent treatment with any other drug / therapy.

The investigator will mention the probable cause of withdrawal and provide possible medical treatment to manage the illness. The patient will be withdrawn if the above said parameters shoot up in his blood picture due to non-compliance.

6.2 Study Drug Supplies:

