7.2 Follow-up Procedure

A prospective observation will be done for a period of one month after completion of the trial (6 months) by both groups. The drug intervention will be withdrawn in the drug group and LSM group will be on normal life style to measure the efficacy of the trial drug and LSM in both the groups. A comparison (physical assessment and blood sugar (OGTT) between the trial and non-trial period will be drawn in the outcome.

8. Safety and Efficacy Assessments

Liver function test and renal function test are recorded before and after trial drug administration to measure the safety of the drug. OGTT, HbA1c and blood glucose levels also measured for efficacy of the drug. Lipid profile is tested to measure the complementary benefit of the drug in microvascular end arterial diseases.

9. Adverse Event Reporting

If any adverse drug reaction or adverse event is reported, the study subject will be referred to the Pharmacovigilance cell of the study centre. According to the advice of the Pharmacovigilance cell withdrawal or continuation of the study will be determined.

10. Statistical Methods/Data Analysis

All the data will be entered in the Microsoft excel and the data will be analyzed using SPSS Version 16. Quantitative data shall be given in mean and standard deviation. Prevalence

shall be given in proportion with 95% confidence interval. Association with risk factors shall be analyzed using chi square test and multivariate analysis. Correlation shall be analyzed using Karl Pearson, with significant level ($P < 0.005$ or $P < 0.05$). Comparison between means with Annovatest, difference between means assessed by paired t test. Further analysis will be extended depending upon the results at the end of the study.

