14. RBC _____ (HPF)
15. Cast _____ (HPF)

Stool examination

16. Routine _____

Microscopic

17. Ova _____ 18. Cyst _____ 19. Occult Blood _____

Blood

20. TC (Cells/Cumm) _____

Differential Count

21. P (%) _____ 22. L (%) _____ 23. E (%) _____ 24. M (%) _____ 25. B (%) _____

26. Hb (g/dl) _____.

27. ESR (1/2 hour.) _____ ESR (1 hour.) _____

28. Blood Sugar- Fasting (mg/dl) _____

29. Blood Sugar – OGTT (mg/dl) _____ (After 2 hours)/ PP _____ (mg/dl)

30. Glycated Hemoglobin (HbA1c) _____ (to be done before treatment and at the end of treatment)

31. Blood Urea (mg/dl) _____

32. S. Creatinine (mg/dl) _____

33. Uric acid (mg/dl) _____

LIPID PROFILE

34. Serum total Cholesterol (mg/dl) _____

35. S. Triglycerides (mg/dl) _____

36. HDL (mg/dl) _____

37. LDL (mg/dl) _____

38. VLDL (mg/dl) _____

LIVER FUNCTION TEST

Serum Bilirubin

39. Total (mg/dl) _____

40. Direct (mg/dl) _____

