41. SGOT (IU/L) _____

- 42. SGPT (IU/L) _____
- 43. Alk. Phosphatase (KA units) _____
- 44. Total proteins (gm/dl) _____
- 45. Albumin (gm/dl) _____
- 46. Globulin (gm/dl) _____
- 47. A/G Ratio _____

Serum Electrolytes

- 48. Sodium (mEq/L) _____
- 49. Potassium (mEq/L) _____
- 50. Chloride (mEq/L) _____

Sl.No.10-50 will be done during I visit (0 day), IV visit (90th day) and VII visit (180th day).

Sl.No.28 & 29 (Blood Sugar- F & PP) in the following visits II, III, V and VI.

Date:

--	--

--	--

--	--

Signature of Investigator/ Medical Officer

**OPEN LABELED RANDOMIZED CONTROLLED CLINICAL TRIAL ON
IMPAIRED GLUCOSE TOLERANCE –IGT (Munneerizhivu)**

**FORM II - CLINICAL & PHYSIOLOGICAL ASSESSMENT
[Before Treatment & During monthly visit]**

1 st visit – 0 day		5 th visit – 120 th day	
2 nd visit – 30 th day		6 th visit – 150 th day	
3 rd visit – 60 th day		7 th visit – 180 th day	
4 th visit – 90 th day		8 th visit – 210 th day	

1. Code No. (Clinical trial)
2. Centre : Siddha Central Research Institute, Arumbakkam, Chennai.
3. Name of the Patient _____
4. S. No. of Patient _____
5. Gender Male (1) Female (2)
6. Date of Birth Age (Years)
7. Address _____

Chief complaint with duration (if any) in days (mostly asymptomatic)

- | | Absent (0) | Present (1) |
|------------------------------------|---|---|
| 8. Polyuria (Excessive Urine) |  |  |
| If present, duration in days _____ | | |
| 9. Polyphagia (Excessive Hunger) |  |  |
| If present, duration in days _____ | | |
| 10. Polydipsia(Excessive Thirst) |  |  |

If present, duration in days _____

11. Exhaustion/Tiredness

If present, duration in days _____

Absent (0)

Present (1)

12. Body ache

If present, duration in days _____

VITAL SIGNS

13. Pulse rate/min

14. Heart rate/min

15. BP(mm of Hg)

 /

16. Temperature °F

 .

PRESENT(1)

ABSENT (2)

17. Cyanosis

18. Anaemia

19. Jaundice

20. Clubbing

21. Lymphadenopathy

22. Oedema

23. Height/cm

 .

24. Weight/Kgs

 .

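### Section 6.1.1 takes participants with persistently diabetic glucose out of the study with no later assessment, so some early progressors have no end-of-treatment values

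*Protocol*

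**What the plan says.** Section 6.1.1 of the Protocol is mandatory and covers both arms: "The investigator shall withdraw the patients from both groups of the study if" fasting glucose goes above 126 mg/dl or "2 hours OGTT blood sugar level increases > 199 mg/dl and are not controllable within 90 days". What follows is limited to this: "The investigator will mention the probable cause of withdrawal and provide possible medical treatment to manage the illness". A closing sentence adds withdrawal when these values climb because of non-compliance, without repeating the 90-day window. Section 9 uses the phrase "withdrawal or continuation of the study will be determined", which supports reading withdrawal as leaving the study and not only stopping the tablets.

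The measurement schedule is in the Form III footer: "Sl.No.10-50 will be done during I visit (0 day), IV visit (90th day) and VII visit (180th day"; and "Sl.No.28 & 29 (Blood Sugar- F & PP) in the following visits II, III, V and VI". Two places are narrower. Form III item 30 says of HbA1c: "to be done before treatment and at the end of treatment". Section 8 says: "Liver function test and renal function test are recorded before and after trial drug administration". Section 7.1 likewise names only pre- and post-treatment testing. The one-month observation in section 7.2 follows completion of the six-month trial.

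The primary endpoint (10.1.1) combines OGTT, fasting glucose and HbA1c. The secondary endpoint (10.1.2) is normal liver and renal tests. Section 11 defines success as not progressing to diabetes.

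**The concern.** The withdrawal trigger overlaps the event the trial is meant to prevent. A participant who meets it early leaves before day 180, and the reason for leaving is the outcome itself. A comparison of day-180 means among completers then omits some of the worst progressors, which flatters whichever arm has more of them. If the drug works, its benefit is diluted; if it worsens glucose, the harm is partly hidden.

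The loss goes beyond glucose. HbA1c is a component of the primary endpoint, and liver and renal tests are the whole of the secondary endpoint. Neither can be rebuilt from glucose readings. A drug-arm participant who leaves at day 120 or 150 has no clearly specified safety test at the end of exposure.

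**Working it through.** **Timing.** Visits fall on days 0, 30, 60, 90, 120, 150, 180 and 210 (Form II). The start of the 90 days is not stated, so both readings were checked.

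- *From the first raised reading:* 30 + 90 = 120, 60 + 90 = 150, 90 + 90 = 180. A fasting rise first seen at day 30 or 60 leads to exit before day 180; one first seen at day 90 still reaches day 180. For OGTT this holds only if OGTT is done at the monthly visits. The footer says F & PP there; if OGTT is done only at days 0, 90 and 180, a rise first seen at day 90 still reaches day 180.
- *First 90 days of the study:* exit falls near day 90 for either test, and day 180 is lost.

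Under both readings some early progressors, not all progressors, lose day 180 and day 210. Their trigger values remain, as does the day-90 panel if the footer governs. For HbA1c, liver and renal tests the day-90 value is uncertain because item 30 and sections 7.1 and 8 do not mention it.

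**Size.** The Protocol gives no rates, SDs or effect sizes, so every input here is an assumption. Simulation: 400,000 per arm, linear change from baseline to day 180, baseline–end correlation 0.5.

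- *Fasting (mg/dl):* baseline normal, mean 112, SD 8, limited to 100–125. Day-180 means drug/control 105/110 and 106/112 (SD 12), 108/113 and 110/116 (SD 14). Within-person SD 5 or 8.
- *OGTT (mg/dl):* baseline normal, mean 165, SD 20, limited to 140–199. Day-180 means 140/155, 145/160 and 150/170 (SD 30) and 140/155 (SD 35). Within-person SD 10–20.

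| Rule | Withdrawn of 30, drug | Withdrawn of 30, control | Shrinkage of completer difference | Shrinkage using last value before withdrawal |
|---|---|---|---|---|
| Fasting >126 at days 30 and 120, or 60 and 150 | 0.35–1.36 | 0.77–2.47 | 4.0–10.8% | −1.7 to 2.1% |
| Same, every reading in between also raised | 0.04–0.43 | 0.11–0.98 | 0.8–7.1% | −0.2 to 1.4% |
| Fasting >126 at day 30 or 60, and at day 90 | 0.28–1.09 | 0.59–1.85 | 2.6–8.5% | −0.8 to 3.7% |
| OGTT >199 at day 90 (one reading; upper end) | 0.49–1.74 | 1.17–3.54 | 5.1–10.7% | −3.8 to 2.7% |

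Largest losses against the standard error, SE = √(2·SD²/30):

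- Fasting: 5.99 − 5.34 = 0.65; SE = √(2·14²/30) = 3.62; 0.65/3.62 = 0.18.
- OGTT: 19.93 − 17.80 = 2.13; SE = √(2·30²/30) = 7.75; 2.13/7.75 = 0.28.

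A repeat under the same assumptions gave about 3–12% shrinkage (3–9% under the strict rule), and the last-value analysis came within about 5%. A separate OGTT simulation (baseline 165, SD 15; mean change −15 v −5; SD of change 25 or 35; monthly OGTT; all four readings across the 90 days raised) withdrew 0.6–2.2% per arm. The difference moved from −9.78 to −9.52 (2.7%) and from −10.14 to −9.57 (5.6%).

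**Binary endpoint, illustration.** With assumed successes of 12/30 v 9/30 the difference is 10.0 points. If 1 drug and 3 control participants leave and only completers count, 12/29 − 9/27 = 41.4% − 33.3% = 8.0 points. Counting those who leave as failures restores 10.0.

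**The case against.** The strongest reply is that little is at stake, and that an analysis plan could handle most of it. Someone with uncontrolled fasting glucose above 126 or OGTT above 199 is already failing the binary endpoint. Section 10 fixes no time point or population for its mean comparisons, and using the last pre-withdrawal value repairs them almost fully. This stands and limits the point to a modest one.

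An exit panel can also be read into the text, since treatment ends when the participant is withdrawn, and exit at study day 90 would coincide with the full panel in the footer. That is a possible reading, but the footer ties the panel to fixed visits and 6.1.1 mentions no test, so the panel is not assured.

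The larger simulated losses come from looser rules than sustained elevation. That is fair: the strict rule gives about 0.2 to 1.4 withdrawn over both arms, and the OGTT row is an upper end. In every scenario simulated the drug works, so the bias is conservative; the reverse direction was not simulated.

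The section heading may also confine withdrawal to non-compliant participants, which would reduce the numbers. Equally, the 90-day condition may attach only to OGTT, or the closing sentence may add withdrawals with no window, which would increase them. The wording does not settle this.

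Finally, extra visits after rescue do not recover on-treatment glucose or HbA1c. That stands, and is why the panel before rescue matters more than the retained visits.

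**Conclusion.** The concern holds. As written, 6.1.1 makes some end-of-treatment data missing because of the outcome, under either reading of the 90 days. The damage to glucose comparisons is small: roughly 1–11% shrinkage of a completer difference in the simulations tabulated, at most about 0.3 of a standard error, and largely repairable from recorded values. The binary endpoint is unbiased if withdrawn participants count as failures. What no analysis rule can restore is HbA1c, liver and renal results that were not drawn.

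This is a cheap improvement that should be made, not a threat to the trial. Confidence is medium: the timing follows from the text, but all magnitudes rest on assumed means, SDs and correlations and on how the trigger is read. The clinical limits themselves are not questioned.

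**What to change.** Reword section 6.1.1 as follows:

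- Meeting the glucose limits stops study treatment and permits rescue care; consenting participants stay in the study and attend the day-180 and day-210 visits.
- At the visit where the trigger is met, and before rescue starts, take OGTT, fasting glucose, HbA1c, liver and renal tests.
- Count these participants as not successful, with all randomised participants in the denominator.
- Use the last pre-rescue glucose values in the on-treatment comparison of means, and flag values obtained after rescue.
- State one start for the 90 days, and apply the trigger whether or not the participant is judged compliant.

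Section 6.3 needs a matching exception, since it currently bars hypoglycaemic agents.

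The cost is protocol wording, one extra blood panel and a few already scheduled visits for about 1–4 participants over both arms (fewer under the strict rule, up to about 5 at the upper end). Reported success rates will look slightly lower than among completers.

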6.2.1 Formulation and Packaging

The sponsor (Investigator) will supply the trial drug and 500 mg of Chooranam in the form of tablet. A plastic container can be given to the study subject, consists of 240 number of tablet for 30 days duration.

6.2.2 Preparing and dispensing

A plastic container can be given to the study subject which contains 240 number of tables for 30 days duration. The study subject has to visit once in 30 days for 180 days duration.

6.2.3 Drug administration

4 tablets before food in the morning and evening with water.

6.3 Concomitant medication:

The study subject should not use any hypoglycemic agents and hypolipidemic agents. Without prior consultation of investigator, the trial subject should not consume any medication for any illness.

7. Research Study Procedures

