1.1 Background

Siddha system is one of the ancient systems of Indian medicine¹. This system focuses on leading a healthy life style based on physical, emotional, psychological and social wellbeing. In AYUSH systems the promotion of preventive approach to achieve the goal of being healthy is attained through holistic treatments. A pre-diabetic state (IFG, IGT, and both) of dysglycemia is defined as IGT which has a strong association with insulin resistance and increased risk of cardiovascular pathology. IGT may precede type 2 diabetes mellitus by many years. It is also a risk factor for mortality². Pre-diabetic stage is treated in contemporary western medicine with hypoglycemic drugs. But lifestyle modifications are treated separately and not approached holistically. Non-diabetic hyperglycemia that does not satisfy the diagnostic criteria for diabetes mellitus (DM) is generally known as prediabetes (preDM). It is generally agreed that all forms of diabetes pass through prediabetes state before escalating into full-blown diabetes⁷. Similar to DM, fasting plasma glucose (FPG) and oral glucose tolerance tests are both used independently as defining criteria for preDM^{7, 8}. Recently, hemoglobin A1c (HbA1c) has also been used in the diagnosis of preDM^{7, 9}. It is well-established that the risks of type 2 DM (T2DM) and cardiovascular disease are significantly increased in preDM subjects. The pooled relative risk for development of new diabetes is 6.02 in people with IGT, 4.70 in people with IFG, and 12.21 in people with both. Earlier evidences have proved that combined effect of diet, exercise and drugs (Metformin, Agarbose) are effective at preventive progression to DM from IGT subjects¹¹. According to DPP study intensive lifestyle intervention reduced the development of diabetes by 58%¹².

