5.1 Criteria for Exclusion:

Subjects with age below 30 and above 60 years are excluded in the study. The subjects are excluded in the study those who are known Diabetes, Malignant and accelerated hypertensive, Chronic Liver and Renal diseases, Coronary artery disease, Secondary Diabetes mellitus, CNS disorder (e.g. encephalopathy) and patient undergoing regular treatment for any other severe illness. Pregnant woman and planning to be pregnant within six months and lactating mother are excluded.

6. Study Drug:

The intervention group receives either trial drug or life style modification. The trial drug is an official Siddha formulation mentioned in Siddha Formulary. Recent animal studies have also proved its anti-diabetic activity. It is a kayakalpa drug having anti-oxidant potential, hypothetically assumed to act in IGT.

Dose: 500 mg Tablet , 4 tablets twice a day. Dose as per the market availability and the dose 4 gm / day is as per Marundhu Alavu Attavanai mentioned in Gunapadam Thatthu Jeeva Vaguppu.

The LSM group will be advised to adopt life style modifications (balanced diet along with brisk walking not less than 150 min/week.) These interventions will be measured via LSM intervention compliance form.

Duration of the medication: 180 days. Duration is to measure the range of HbA1c.

6.1 Study drug Compliance/Adherence:

The container will be checked and the tablets will be counted by which compliance will be checked during each and every visit. It can also be assessed based on the drug compliance

form (Form IV A) for drug intervention group. The LSM group can be assessed based on the LSM intervention compliance form (Form IV B).

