7.1 Screening procedures

The full details of history, physical examination, anthropometric measurements, 24-hours diet recall, physical activity of the patients will be recorded as per the proforma. OGTT is the critical investigation for this study and based on this the screening will be done. Investigations - HbA1c and Fasting blood sugar, Lipid profile, Liver function test, Renal function test, Electrolytes and Urine analysis will be taken before and after treatment and the reports will be recorded.

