8. The Diabetes prevention program (DPP) Research Group. *Diabetes care*, 2002, 25:2165-2171.

**OPEN LABELED RANDOMIZED CONTROLLED CLINICAL TRIAL ON
IMPAIRED GLUCOSE TOLERANCE –IGT (Munneerizhivu)**

FORM I - SCREENING PROFORMA

1. Code No (of clinical trial)
2. Centre: _____
3. Name of the Patient _____
4. S. No. of Patient _____
5. Gender Male (1) Female (2)
6. Date of Birth Age (Years)
7. Address _____

Mobile:

Phone no:

CRITERIA FOR INCLUSION

Yes (1)

No (0)

- | | | |
|---|----------------------|----------------------|
| 8. Age between 30 years and 60 years |  |  |
| 9. OGTT – After 2 hours < 140 mg and > 199 mg |  |  |
| 10. Glycated hemoglobin (HBA1C) >6.0% and <6.5% |  |  |

11. Blood sugar – Fasting > 100 and =< 125 mg/dl

CRITERIA FOR EXCLUSION

12. Age below 30 and above 60 years.

13. Malignant and accelerated hypertensive

14. CVS disorder (CAD)

15. Pregnant woman or the women planning to be pregnant in next six months

16. Lactating mothers

17. Secondary Diabetes mellitus

18. Patient undergoing regular treatment for Diabetes or for any other severe illness

19. CNS disorder e.g. encephalopathy

If yes to S.No.8-11 admit the patient into the study.

If admitted subject _____ No. _____

Date: _____

Signature of the Doctor _____

**OPEN LABELED RANDOMIZED CONTROLLED CLINICAL TRIAL ON
IMPAIRED GLUCOSE TOLERANCE –IGT (Munneerizhivu)**

FORM I A – SELECTION PROFORMA

1. Code No. (Clinical trial)
2. Centre :
3. Name of the Patient _____
4. S. No. of Patient _____
5. Gender Male (1) Female (2)
6. Date of Birth Age (Years)
7. Address _____

8. Educational status
Illiterate (1) Read & Write (2)
Educational qualifications _____ (3)
9. Occupation
Desk Work (1) Field Work (2) Others Specify _____
10. Income per capita per month in ₹ _____

Chief complaint with duration (if any) in days (mostly asymptomatic)

- | | Absent (0) | Present (1) |
|------------------------------------|----------------------|----------------------|
| 11. Polyuria (Excessive Urine) |  |  |
| If present, duration in days _____ | | |
| 12. Polyphagia (Excessive Hunger) |  |  |
| If present, duration in days _____ | | |
| 13. Polydipsia(Excessive Thirst) |  |  |
| If present, duration in days _____ | | |

Absent (0)

Present (1)

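### Form I admits on the inclusion items alone, contrary to Section 5.1, and some users of the drugs that Section 6.3 bars remain eligible

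*Protocol*

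**What the plan says.** - **Ban on study (Protocol, Section 6.3).** "The study subject should not use any hypoglycemic agents and hypolipidemic agents". No washout or look-back period is given. The next sentence adds: "Without prior consultation of investigator, the trial subject should not consume any medication for any illness".
- **Exclusions (Section 5.1).** The list names diseases, among them known diabetes and coronary artery disease, and also "patient undergoing regular treatment for any other severe illness". It names no drug class.
- **Exclusions (Form I, items 12-19).** The nearest item is 18: "Patient undergoing regular treatment for Diabetes or for any other severe illness". Again no drug class is named as such.
- **Admission line (Form I).** "If yes to S.No.8-11 admit the patient into the study". Items 8-11 are the inclusion items. The line does not mention items 12-19.
- **Sampling (Form III).** "Sl.No.10-50 will be done during I visit (0 day), IV visit (90th day) and VII visit (180th day)". These items include fasting and 2-hour glucose, HbA1c and the lipid profile. The note beside HbA1c itself names only the start and end of treatment, so day 0 and day 180 are common to both statements.
- **Screening (Section 7.1).** The record is to hold "The full details of history, physical examination, anthropometric measurements", among other items.

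**The concern.** There are two linked faults. First, the form that decides entry states a rule that differs from the protocol body: anyone who meets the inclusion items is to be admitted, whatever is ticked under the exclusions. Second, a ban that starts after entry has no full counterpart at entry. A person who already takes a barred agent can be enrolled and then cannot comply without stopping it.

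Two things are at stake. A participant may stop a prescribed agent because of the trial. And that participant's day-0 value is on the agent while the later values are off it, so a before-after change within an arm mixes the study intervention with drug withdrawal. This applies most plainly to lipids, and possibly to glucose and HbA1c.

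**Working it through.** **Step 1: the admission line against Section 5.1.** Section 5.1 says that subjects with the listed conditions are excluded. Form I prints its exclusion list as items 12-19 but makes admission depend on items 8-11 only. The two rules give different answers for any patient with 'yes' to items 8-11 and 'yes' to, say, item 14 (coronary artery disease) or item 15 (pregnancy). This is a contradiction in the text and needs no calculation.

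**Step 2: who is covered by the exclusions.**
- Hypoglycaemic agent taken for diabetes: excluded by 'known diabetes' in Section 5.1 and by item 18.
- Hypoglycaemic agent taken for pre-diabetes: not covered. Section 1.1 makes this group plausible: "Pre-diabetic stage is treated in contemporary western medicine with hypoglycemic drugs".
- Lipid-lowering agent in a person with coronary artery disease or under regular treatment for a severe illness: excluded.
- Lipid-lowering agent in anyone else: not covered.
- Either class, recently stopped: not addressed as such.

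**Step 3: what follows for an uncovered user.** The person meets the criteria, is sampled on day 0 while on the agent, falls under Section 6.3 as a study subject, and is sampled again on days 90 and 180 off the agent.

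**Step 4: within-arm effect, illustration only.** The only input from the documents is n = 30 per arm (Section 10.2). Assumed inputs: k = 1 to 3 users in an arm, LDL rise on stopping d = 20 to 40 mg/dl, SD of change 20 to 40 mg/dl.
- Shift in the arm's mean change = k × d / 30. Smallest: 1 × 20 / 30 = 0.67 mg/dl. Largest: 3 × 40 / 30 = 4.00 mg/dl.
- 95% CI half-width = t(0.975, 29 df) × SD / √30, with t = 2.045. SD 20: 7.47 mg/dl. SD 40: 14.94 mg/dl.
- Shift over half-width: from 0.67 / 14.94 = 4.5% to 4.00 / 7.47 = about 54%. The upper end needs the most users, the largest rise and the smallest SD together.

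The width of this range shows that the documents do not fix a size. No figure is offered for glucose or HbA1c.

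**Step 5: between-arm effect.** Users enter before random allocation. With K users among 60 split 30:30, each arm expects K × 30 / 60 = K / 2, so the expected difference is 0. This assumes that Section 6.3 is applied alike in both arms.

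**The case against.** The strongest reply is that the form is being read too literally. Item 9, one of the four items that must be 'yes', asks for a 2-hour value both below 140 and above 199, which nobody can meet. If that item is read with common sense, the admission line deserves the same treatment. The exclusion items stand under their own heading, and Section 5.1 governs. Likewise, Section 6.3 can be read to mean that a current user is simply not enrolled, and the history taken under Section 7.1 may well reveal such use.

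Much of this stands. A reader might infer that patients with listed exclusions will be enrolled. The documents do not support that, because Section 5.1 and the form's own heading make it unlikely. It remains true that an operational form states a rule at odds with the protocol body.

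A reader might also infer that hypoglycaemic use in general is left open. It is not: known diabetes in Section 5.1 and item 18 of Form I already exclude most such users. The gap is use outside diabetes, and lipid-lowering use without an excluded disease. History-taking may bring such use to light, but no entry criterion then acts on it, and Section 6.3 is worded for people already in the study.

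**Conclusion.** The point holds in a narrow form and is minor. The admission line contradicts Section 5.1, and two groups of users of barred agents remain eligible although they cannot comply with Section 6.3 without stopping the agent.

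A reader might go further and conclude that the treatment comparison is biased. The documents do not support this. Allocation is random (Section 3.1), so users are balanced between arms in expectation. The primary endpoint (Section 10.1.1) is a set of thresholds on treatment-period or later values and not a change from day 0. Lipids are neither a primary nor a secondary endpoint; Section 8 treats them as an additional benefit. Section 10 plans a paired t test but does not say for which variables.

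What remains is possible distortion of within-arm before-after changes, probably in the direction of hiding a benefit, and participants who give up a prescribed agent. Both depend on how many such users present, which the documents do not say. The LDL figures above rest on assumed inputs and are not an estimate for this trial.

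**What to change.** 1. Reword the Form I admission line to: 'If yes to S.No. 8-11 and no to all exclusion items, admit the patient into the study'.
2. Add to Section 5.1 and to the Form I exclusion list: 'current use of any hypoglycaemic or hypolipidaemic agent, or use within 90 days before day-0 sampling'. The 90 days are an assumption, chosen to match the 90-day interval at which Form III repeats HbA1c. The sponsor may prefer another length, but one should be stated.

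Both changes are needed, since a new exclusion item would not bind under the present admission line. The new Form I item can also record the agent and the date of the last dose. The cost is one line in Section 5.1, one item on Form I and one reworded sentence. The downside is that a few screened candidates become ineligible.
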